3.6.3. Other Exploratory Endpoints

[REDACTED]

[REDACTED]

[REDACTED]

[REDACTED]

A large black rectangular redaction box covers the majority of the page content, from approximately y=113 to y=294. The redaction is irregular, with jagged edges and a small white triangular cutout on the right side.

3.7. Safety Analyses (Part A and Part B)

The safety analysis will be carried out using the Safety Population that includes all randomized subjects who receive at least one dose of study drug (ALKS 8700 or DMF).. Safety assessments

will be summarized using descriptive statistics along with supportive listings based on observed values. Listings will be provided for all safety parameters.

3.7.1. Adverse Events

All adverse events (AEs) will be coded by System Organ Class (SOC) and Preferred Term (PT) using the Medical Dictionary for Regulatory Activities MedDRA version 20.1. The verbatim term will be included in the AE listings.

AEs will be identified as emerging in the treatment period and the follow up period. During the treatment period, an AE will be considered a treatment-emergent AE (TEAE) if the event starts or worsens on or after the date of first dose of study drug in the current trial. The Treatment Period is defined as the period from the first dose date to last dose date plus 1 day, inclusive.

During the follow up period, post-discontinuation emergent AEs (PDEAEs), defined as AEs that started or worsened after the last dose date plus 1 day, will be summarized. For PDEAEs, the greatest severity on or before the last dose date plus 1 day will be used as the benchmark for the comparison of the AEs occurring during the follow up period. The Follow-up Period is defined as the period between the date of the last dose date plus 2 day and the last study date, inclusive.

An overview table, including number of subjects with TEAEs, serious AEs (SAEs), AEs leading to study discontinuation, and study drug-related TEAEs will be provided. Adverse events leading to study discontinuation and SAEs leading to death will be summarized in the period when the discontinuation or death occurred.

The following summary tables will be provided for the treatment period by treatment group and overall:

- TEAEs by SOC and PT
- TEAEs by SOC, PT, and severity
- TEAEs by SOC, PT, and relationship
- Study drug related TEAEs by SOC and PT
- TEAEs experienced by $\geq 5\%$ of subjects by SOC and PT
- TEAEs experienced by $\geq 2\%$ of subjects by SOC and PT
- SAEs by SOC and PT
- AEs leading to study discontinuation by SOC and PT

All AE tables will be sorted by SOC and then PT in decreasing frequency based on all subjects in the Safety Population.

A subject having the same AE (as determined by the coded MedDRA PT) more than once will be counted only once in the number and percentage of subjects' calculation for that AE.

Similarly, if a subject has more than one AE in an SOC, the subject will be counted only once in the total number of subjects with an AE for that SOC. If a subject has the same AE on multiple occasions, the highest severity (severe > moderate > mild) recorded for the event will be presented in the AE by severity summary. Similarly, if a subject has the same AE on multiple occasions, the closest relationship to study drug (related > not related, where related includes

definitely related, probably related, and possibly related; and not related includes probably not related and definitely not related) recorded for the event will be presented in the AE by relationship summary.

The following summary tables will be provided for flushing and flushing-related TEAEs and GI SOC only by treatment group and overall:

- TEAEs by PT and outcome
- Duration of TEAEs among those resolved by PT
- Time to onset of TEAEs by PT

PTs for flushing and related AEs include: flushing; hot flush; erythema, generalized erythema, burning sensation, skin burning sensation, feeling hot, pruritus; pruritus generalized; rash, rash pruritic, rash maculo-papular; rash macular; rash papular.

If a subject has the same AE on multiple occasions, the worst outcome (not resolved > resolved, where resolved includes recovered/resolved and recovered/resolved with sequelae; and not resolved includes not recovered/not resolved and fatal) recorded for the event will be presented in the AE by outcome summary. For duration and time to onset, if a subject has the same AE on multiple occasions, the first presentation will be used in summarizing time to onset and the mean duration of the multiple AE events will be used in summarizing duration.

All AEs will be included in the listings. Supporting listings of SAEs, AEs leading to study discontinuation, and AEs leading to death will be provided. Subjects with PDEAEs in the Follow-up Period will also be listed.

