The study duration for each part is approximately 11 weeks, which includes up to 4 weeks for screening (including a 1-week lead-in period), a 5-week double-blind treatment period (with 1-week titration), and a 2-week follow-up period (for subjects not continuing into the ALK8700-A301 long-term safety study). During the 5-week treatment period (Visits 3-8),

subjects will return to the clinic for weekly scheduled visits for assessments of safety, tolerability, pharmacokinetics (in a subset of subjects in Part A at selected sites), and clinical status (see [Figure 1](#)). Any subject who prematurely discontinues from the study will return to the clinic for an ET visit (Visit 8) and a follow-up visit (Visit 9).

Subjects completing the entire 5 weeks of double-blind treatment in either Part A or Part B of the study will be eligible to enroll in a long-term, open-label safety study (Study [ALK8700-A301](#)) and receive ALKS 8700 for up to 96 weeks. Subjects not enrolling in the long-term safety study will return to the clinic 2 weeks following Visit 8 for a follow-up visit (Visit 9).

A schematic of the study design is provided in [Figure 1](#) below.

Figure 1: Study Design Schematic (Part A and Part B)

*Subjects completing the 5-week treatment period will either continue into the ALK8700-A301 long-term safety study or enter the safety follow-up period and return to Visit 9

[REDACTED]

Table 1: Schedule of Visits and Assessments

Visit	Screening		5-Week Randomized Treatment ¹							Follow-up
	1 ²	2 ³	3	4	5	6	7	8 (ET)		
Week	-4	-1 (±2 days)	1 (±3 days)	2 (±3 days)	3 (±3 days)	4 (±3 days)	5 (±3 days)	6 (±3 days)	7 (±3 days)	8 (±3 days)
Informed Consent	X									
Eligibility Criteria Review	X		X ⁴							
Demographics	X									
Medical History	X									
Height	X									
Weight	X		X ⁴						X	
Physical Exam ⁵	X		X ⁴						X	X
Concomitant Medication Review	X	X	X	X	X	X	X	X	X	X
Adverse Event Monitoring	X	X	X	X	X	X	X	X	X	X
Serology Testing ⁶	X									
Pregnancy Test ⁷	X		X ⁴							
Vital Signs ⁸	X		X ⁴	X	X	X	X	X	X	X
Standard 12-Lead ECG ⁹	X		X ⁴		X				X	X
Biochemistry, Urinalysis, & Hematology Samples ¹¹	X		X ⁴		X				X	X

Table 1: Schedule of Visits and Assessments (Continued)

	Screening		5-Week Randomized Treatment ¹							Follow-up 9
	1 ²	2 ³	3	4	5	6	7	8 (ET)		
Visit	1 ²	2 ³	3	4	5	6	7	8 (ET)	9	
Week	-4	-1 (±2 days)	1 (±3 days)	2 (±3 days)	3 (±3 days)	4 (±3 days)	5 (±3 days)	6 (±3 days)	7 (±3 days)	8 (±4 days)
Brain MRI	X ¹²									

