3. DATA ANALYSIS

3.1. General Statistical Methodology

The safety and efficacy endpoints will be summarized by treatment group and overall as described below. In general, summary statistics (n, mean, standard deviation [SD], median, minimum, and maximum for continuous variables, and number and percentage of subjects in each category for categorical variables) will be provided by treatment group and overall. All summary tables will be based on observed data, and missing values will not be imputed unless otherwise indicated. Measurements collected from unscheduled visits or repeated assessments will not be included in the by-visit summary tables or figures, but will be included in the analyses for the potentially clinically significant (PCS) post-baseline values and subject listings. Source data for the summary tables and statistical analyses will be presented as by-subject data listings.

Baseline value is defined as the last non-missing assessment prior to the first dose of study drug.

All statistical tests and confidence intervals (CIs), unless stated otherwise, will be 2-sided and will be set at an alpha level of 0.05.

All the efficacy analyses will be summarized by the planned treatment assignment, and all the safety analyses will be summarized by actual treatment.

The data will be summarized for the following two study periods as appropriate.

- Treatment Period, which is defined as the period between the first dose date after randomization and the last dose date plus 1 day, inclusive.
- Follow-up Period, which is defined as the period between the date of the last dose date plus 2 day and the last study date, inclusive.

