3.7.2. Deaths, Serious and Other Significant Adverse Events

The number and percentage of subjects with at least one SAE (regardless treatment emergent or not) will be summarized by SOC and PT for the Safety Population. Deaths and AEs leading to discontinuation (regardless treatment emergent or not) will be summarized similarly.

Supporting listings of serious AEs and AEs leading to study discontinuations will be provided. Subjects who died during the study will also be listed.

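### Section 3.7.1 assigns AEs leading to study discontinuation by exit date rather than onset, so an on-drug event can drop out of the treatment-period discontinuation table

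*SAP*

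**What the plan says.** Section 3.7.1 of the SAP sets two period boundaries. For treatment: "The Treatment Period is defined as the period from the first dose date to last dose date plus 1 day, inclusive". Section 3.1 gives the same definition. The Follow-up Period is "the period between the date of the last dose date plus 2 day and the last study date, inclusive".

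Within these periods AEs are classified by onset or worsening. A TEAE starts or worsens on or after the first dose. A post-discontinuation emergent AE (PDEAE) starts or worsens later than one day after the last dose. The paragraph on the overview table then adds a different rule for two kinds of event: "Adverse events leading to study discontinuation and SAEs leading to death will be summarized in the period when the discontinuation or death occurred".

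The list of AE tables that follows is introduced with "The following summary tables will be provided for the treatment period by treatment group and overall", and one of its entries is "AEs leading to study discontinuation by SOC and PT".

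Section 3.7.2 has a second display of the same outcome: "Deaths and AEs leading to discontinuation (regardless treatment emergent or not) will be summarized similarly".

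**The concern.** This trial compares the GI tolerability of two drugs, so withdrawal because of an adverse event is a result that readers will look for. The treatment-period table is where they would expect to find withdrawals caused by events that arose on drug.

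Under the exception in section 3.7.1, onset on drug is not enough for an event to enter that table. The discontinuation itself must also fall no later than one day after the last dose. The rule refers to leaving the study, not to stopping the drug. Section 1.2 has early leavers come back for an early-termination visit and then a follow-up visit, so contact with the subject continues after dosing ends. Two subjects with the same event, the same onset and the same last dose could be tabulated differently only because their exits were dated differently.

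For fatal SAEs the date of death is clear, but the logic is the same: an event that began on drug is placed in follow-up if death comes two or more days after the last dose.

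**Working it through.** No figure in the SAP bears on this point, so there is none to reproduce. The check is date logic.

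**Inputs**
- L = date of last dose.
- Treatment Period: first dose to L + 1 (sections 3.1 and 3.7.1).
- Follow-up Period: L + 2 to last study date (same sections).
- D = date of study discontinuation. The SAP does not define it. It could be the decision to withdraw, the last dose, the early-termination visit or the last study date.
- The AE starts on or before L.

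**Placement under the present rule**
- If D is L or L + 1, the AE stays in the treatment-period discontinuation table.
- If D is L + 2 or later, the AE is assigned to the Follow-up Period and leaves that table.

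**Illustration (assumed dates).** The last dose is on Day 10, so the Treatment Period ends on Day 11 and follow-up starts on Day 12. If the exit is dated Day 10 or 11, the AE is in the table. If it is dated to an early-termination visit on Day 13, the same AE is not.

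**Where a moved event goes**
- Section 3.7.1 lists no follow-up table of AEs leading to discontinuation.
- The event is not a PDEAE unless it worsens after L + 1, so the PDEAE summary does not normally pick it up.
- It remains in the TEAE tables, which go by onset or worsening, in the section 3.7.2 summary and in the listings. Section 3.7.3 also presents GI AEs leading to discontinuation as a category of special interest, without naming a period.
- The overview table reports AEs leading to study discontinuation too, and the exception is the next sentence after it. It may be affected in the same way, but the text does not settle this.

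**Size.** The SAP gives neither an expected withdrawal rate nor an interval from last dose to exit. Purely as an illustration, take 250 randomized subjects per arm (60 + 190, section 2) and assume that 5% withdraw for an AE:

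0.05 × 250 = 12.5 subjects.

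| Assumed share with D ≥ L + 2 | Subjects left in the table | Rate shown |
|---|---|---|
| 0% | 12.5 | 5.0% |
| 50% | 6.25 | 2.5% |
| 80% | 2.5 | 1.0% |
| 100% | 0 | 0% |

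The 5% and all the shares are assumptions. The table shows only that the reported rate can run from the full rate down to zero, depending on a date that the SAP leaves open.

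**The case against.** The strongest reply is that nothing need move at all. Section 1.2 can be read as saying that the subject discontinues first and attends the early-termination visit afterwards. The disposition list in section 3.2.2 has a category for subjects who leave the study during the treatment period, so the sponsor evidently expects some exits to fall there. If the exit is dated at the last dose or the next day, the table is complete. This stands, and it is why the point is that events can drop out, not that they do. A reader might infer that study exit is normally dated two or more days after the last dose. The SAP gives no interval that would support this.

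A reader might also infer that no table shows on-drug events leading to withdrawal. That goes too far. The section 3.7.2 summary includes every such event whatever its exit date. What it does not do is separate on-drug events from those that arose at other times.

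Nor are the two sections in contradiction because their counts may differ. One display is limited to a period and the other is expressly not. The worry that 3.7.2 lets in events from before the first dose is minor: its SAE summary is for the Safety Population, which requires a dose, and the discontinuation summary is to be done in the same way.

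Finally, the rule covers all AEs, not only GI events. It applies alike to both arms, and no between-arm distortion is shown. The AE summaries are descriptive, and the diary-based primary and secondary endpoints are untouched.

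What the reply does not remove is the rule itself. It is a written instruction that departs from the SAP's own classification by onset or worsening, and it rests on an undefined date with a margin of one day.

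**Conclusion.** The point holds in conditional form. Section 3.7.1 uses the date of exit or death to place AEs leading to study discontinuation and fatal SAEs, while other AEs are placed by onset or worsening. An on-drug AE that led to withdrawal can therefore be missing from the treatment-period discontinuation table, and possibly from the overview, when the exit is dated last dose + 2 or later.

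The share affected could be anything from 0% to 100% and cannot be narrowed from the SAP. The consequence is a summary that may be misclassified, not lost data. It should be corrected because the table bears on tolerability and the correction is nearly free.

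**What to change.** In section 3.7.1, replace the exception with a rule of this kind: AEs leading to study discontinuation and fatal SAEs are summarized in the period in which the AE started or worsened, the Treatment Period running from first dose to last dose + 1 day.

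Keep the section 3.7.2 table as it is and label it as the all-events summary. It should not be restricted to events with onset on or after the first dose, because that would remove pre-existing events that worsened on drug and led to withdrawal, which the TEAE definition counts.

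Defining the discontinuation date alone would remove the ambiguity, but the table would still depend on exit timing, so it is the weaker remedy.

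The cost is one sentence and one table label. No new data are needed, since onset and worsening must already be dated to determine TEAE status. The treatment-period discontinuation count may rise. An event that began before the first dose and never worsened would appear only in the 3.7.2 summary and the listings.

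### Summarizing the duration of GI and flushing-related TEAEs only among resolved events biases duration short and can attenuate a difference between arms

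*SAP*

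**What the plan says.** SAP section 3.7.1 introduces a set of three tables with "The following summary tables will be provided for flushing and flushing-related TEAEs and GI SOC only by treatment group and overall". One is "TEAEs by PT and outcome", another is "Duration of TEAEs among those resolved by PT", and the third is time to onset.

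Two rules govern repeated episodes of one PT in the same subject. For the outcome table the worst outcome counts, where "not resolved includes not recovered/not resolved and fatal". For the duration table, "the mean duration of the multiple AE events will be used in summarizing duration". The section also says "All AEs will be included in the listings", so unresolved events appear there.

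Section 3.7 sets the general approach: safety assessments "will be summarized using descriptive statistics along with supportive listings based on observed values". Section 1.2 describes "a 5-week double-blind treatment period (with 1-week titration), and a 2-week follow-up period". The follow-up visit applies to subjects who do not continue into A301 and to those who stop early.

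**The concern.** An event enters the duration table only if its end was seen. For a given onset day, a longer event is less likely to end before the subject's last contact, so the table favours short events. Section 3.7.1 has no rule that uses the time already observed on an unresolved event. An arm with truly longer events loses more of them, which draws the two summaries together.

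The end of observation also varies. The same event, starting on the same day, can count as resolved in a subject seen at Visit 9 and be left out in a subject who rolled over at Visit 8. The resolved-only mean thus depends partly on who rolled over.

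The trial sets out to compare GI tolerability between two active drugs, so a reader will compare these durations across arms even though nothing is tested on them.

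**Working it through.** The SAP states no event duration, no share resolved and no between-arm difference in duration, so there is no figure of its own to reproduce. What follows illustrates size only.

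**Inputs from the SAP (section 1.2).** Treatment lasts 5 weeks, so observation ends at about C = 35 days for a subject who rolls over. With 2 weeks of follow-up, C = 49 days.

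**Assumptions, not from the SAP.** Onset day u is exponential with mean 10 days, truncated at 35, with density g(u) = exp(-u/10) / [10(1 - exp(-3.5))]. Duration is exponential with mean m. The true ratio of means is 2.0, and both arms share the same C.

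**Formulas.**

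- Share resolved: P = ∫ g(u) [1 - exp(-(C-u)/m)] du, for u from 0 to 35.
- Mean among resolved: (1/P) ∫ g(u) [m - (m + C - u) exp(-(C-u)/m)] du.

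**Results.**

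| True means (days) | C | Resolved, % | Resolved-only means (days) | Ratio shown |
|---|---|---|---|---|
| 2 vs 4 | 35 | 99 vs 98 | 1.98 vs 3.86 | 1.95 |
| 2 vs 4 | 49 | 100 vs 100 | 2.00 vs 3.99 | 1.99 |
| 3 vs 6 | 35 | 99 vs 96 | 2.94 vs 5.50 | 1.87 |
| 3 vs 6 | 49 | 100 vs 100 | 3.00 vs 5.90 | 1.97 |
| 5 vs 10 | 35 | 97 vs 89 | 4.72 vs 7.86 | 1.66 |
| 5 vs 10 | 49 | 100 vs 97 | 4.96 vs 9.13 | 1.84 |
| 14 vs 28 | 35 | 81 vs 59 | 9.31 vs 11.55 | 1.24 |
| 14 vs 28 | 49 | 93 vs 75 | 11.46 vs 15.52 | 1.35 |

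**Other shapes.** With onset uniform over days 0-14 or 0-28, and exponential or lognormal (sigma 1.2) durations, a true ratio of 2.0 appears as:

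- 1.74-2.00 for 2 vs 4 days
- 1.54-1.87 for 5 vs 10 days
- 1.31-1.52 for 10 vs 20 days
- 1.20-1.43 for 15 vs 30 days

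The shorter-lasting arm stayed shorter in every scenario.

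**Effect of the cutoff alone.** With one true mean of 14 days, the resolved-only mean is 9.31 days at C = 35 and 11.46 days at C = 49. That gap of about 2.1 days comes only from how long subjects were watched.

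**What a censored summary would target.** For exponential durations the median is m × ln 2: 14 × 0.693 = 9.7 days and 28 × 0.693 = 19.4 days, a ratio of 2.0. Both lie inside the observation window for events with early onset.

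**Repeated episodes.** Take a subject with one resolved and one unresolved episode of the same PT. The outcome rule classes this subject as not resolved. The duration rule averages the episodes. Section 3.7.1 does not say whether the subject enters the duration table or, if so, which episodes are averaged. Two programmers could produce different tables.

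**The case against.** The strongest reply is that the plan already deals with unresolved events openly. The table's title declares its restriction. The outcome table beside it gives, by PT and arm, the number of subjects with an unresolved event, and the listings show every event. In the 14 versus 28 day case at day 35, that table would show a gap of about 22 percentage points in the share resolved (81% against 59%, if the share by event carries over to subjects). The duration table would still point the right way. AE duration is not among the primary or secondary endpoints in section 3.6.2. Those rest on IGISIS and GGISIS scores, and section 3.6.2.1 carries an ongoing IGISIS symptom's score forward until the symptom ends.

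Most of this stands. A reader might infer that the plan discards the longest events and hides a difference between arms. The document does not support that: unresolved events are counted and listed, and the contrast in the scenarios is attenuated, not removed. Nor are the excluded events always long. With a mean duration of 5 days in the model above, the fraction of events unresolved at day 35 that began after day 28 is (exp(3.5) - exp(2.8)) / (exp(3.5) - 1) = 0.52.

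What the reply does not meet is that the outcome table holds counts and no time. A percentage unresolved and a resolved-only mean cannot be combined to recover duration by arm. The IGISIS analyses do not describe AE duration and do not cover flushing.

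**Conclusion.** The point holds as a modest one. The resolved-only table understates duration in both arms and can shrink a between-arm contrast, unevenly so because follow-up ends at different times. The loss is slight if these events last a few days and substantial if they last two weeks or more. The SAP does not say which applies, and the figures rest on assumed onset and duration distributions. They also assume the same end of observation in both arms. If roll-over differed between arms, the cutoff alone could create or distort a difference, but nothing in the document shows that it does.

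It would go too far to call this an error that affects the trial's main comparison. The table is descriptive, no test or superiority claim depends on it, and its restriction is stated. The gap for subjects with mixed outcomes is a separate, small ambiguity that needs a sentence.

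**What to change.** In SAP section 3.7.1:

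- Add a Kaplan-Meier summary of time to resolution by PT and treatment group for the same GI SOC and flushing-related TEAEs. Censor unresolved events at the subject's last contact in this study, and present it next to the outcome table.
- Define the unit for repeated episodes, for example the first episode per subject and PT.
- State how a subject with both resolved and unresolved episodes of one PT enters each table, and how a fatal outcome is treated.
- Keep the resolved-only table as supplementary.

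The cost is a few lines of text and one more table, built from event dates, outcomes and last contact dates. Medians may not be estimable for rare PTs; report them as such, with the number of events and the number censored. Censoring also assumes that the end of observation is unrelated to remaining duration, which a footnote should say, since the choice to roll over could depend on ongoing symptoms.
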